2.1.3 Recruitment Strategies

Study participants will be recruited from the population of patients screened in the lymphoid malignancies clinic of the National Institutes of Health. These will include both referrals from outside physicians as well as patient self-referrals. This study will be posted on NIH websites: <http://ccr.cancer.gov/Lymphoid-Malignancies-Branch> and <http://ClinicalTrials.gov>, on NIH social media forums (Lymphoid Malignancy Branch and NIH social media accounts).

2.2 SCREENING EVALUATION

2.2.1 Screening activities performed prior to obtaining informed consent

Minimal risk activities that may be performed before the subject has signed a consent include the following:

- Email, written, in person or telephone communications with prospective subjects
- Review of existing medical records, including medical history, physical evaluations, laboratory studies, etc.
- Review of existing MRI, x-ray, or CT images
- Review of existing photographs or videos
- Review of existing pathology specimens/reports from a specimen obtained for diagnostic purposes.

If felt to be possible candidates after review of the above and after subjects sign a research consent for screening, they will undergo the evaluations described in Section [2.2.2](#).

2.2.2 Screening activities performed after a consent for screening has been signed

The following screening activities will be performed only after the subject has signed the consent for study 01-C-0129 on which screening activities will be performed.

Assessments and procedures to confirm study eligibility should be completed within 28 days prior to registration (unless otherwise noted). Assessments performed at outside facilities or on another NIH protocol within the timeframes below may also be used to determine eligibility once

Abbreviated Title: IL-15+Mogamulizumab

Version Date: 11/16/2020

a patient has signed the consent. See also the Study Calendar provided in Section [3.7](#). Clinical Evaluations

- Disease history, including: diagnosis, treatment (e.g., systemic treatments, radiation and surgeries), disease status, and significant prior/ongoing side effects and symptoms
- Complete medical history, including: all active conditions considered to be clinically significant by the treating investigator
- Physical examination, including: height (screening only), weight, vital signs (i.e., temperature, pulse, respiratory rate, and blood pressure); review of concomitant medications and symptoms/side effects; and, assessment of performance status

2.2.3 Laboratory Evaluations

NOTE: Results from outside NIH are accepted.

- CBC with differential and reticulocyte count
- Chemistry panels (as noted) or specific analyte required for eligibility, including: Creatinine (i.e., Acute Care Panel); serum calcium, phosphate, magnesium and albumin (i.e., Mineral Panel); ALT, AST, total and direct (if required due to elevated total bilirubin, at discretion of the lab) bilirubin (i.e., Hepatic Panel); 24-hour urine creatinine clearance (if needed to measure CrCl in cases where serum creatinine >1.5mg/dl); and LDH
- Coagulation panel, including: PT/INR and a PTT
- Thyroid function tests (thyroid stimulating hormone (TSH), with free thyroxine (T4) if TSH is abnormal)
- Hepatitis B surface antigen (HBsAg), Hepatitis B core antibody, Hepatitis C antibody (HCV) [qualitative], HIV 1/2 antibody (qualitative) and HTLV-1/2 serologies (within 3 months) **NOTE:** For individuals with a positive hepatitis B core antibody, HBV DNA PCR will be performed to screen for subclinical infection. For individuals with positive hepatitis C antibody and history of curative treatment, HCV DNA PCR will be performed to confirm the resolution of infection.
- Urinalysis (with microscopic examination if abnormal)
- Antinuclear antibody (ANA), rheumatoid factor (RF) and anti-thyroid antibody
- Creatine phosphokinase (CPK), troponin
- Serum or urine pregnancy test (B-HCG) for women of childbearing potential
- Clonal T-cell receptor rearrangement by PCR

2.2.4 Imaging Studies

NOTE: Results from outside NIH are accepted. Other body areas may be imaged if clinically indicated.

- CT neck, chest, abdomen and pelvis (CT should be performed with IV and PO contrast, unless patient is allergic or has renal insufficiency; other imaging may be substituted at the discretion of the investigator [such as MRI])
- PET/CT torso (extremities to be included if there is confirmed or suspected disease involvement)
- MRI of brain (only in patients with suspected involvement of CNS)

Abbreviated Title: IL-15+Mogamulizumab

Version Date: 11/16/2020

2.2.5 Cardiac Evaluation (within 3 months)

- Electrocardiogram (EKG)
- Transthoracic echocardiogram (TTE)

2.2.6 Other Procedures

- Pathologic review/confirmation of diagnosis by Laboratory of Pathology, NCI (no time limit). If archival sample is not available, a fresh tumor biopsy and/or peripheral blood sample will be obtained.
- Pulmonary function tests (PFTs): diffusing capacity/alveolar volume (DLCO/VA), forced expiratory volume in 1 second (FEV1) for patients with significant pulmonary or smoking history

2.3 PARTICIPANT REGISTRATION AND STATUS UPDATE PROCEDURES

Registration and status updates (e.g. when a participant is taken off protocol therapy and when a participant is taken off-study) will take place per CCR SOP ADCR-2, CCR Participant Registration & Status Updates found [here](#).

2.3.1 Screen Failures

Screen failures are defined as participants who consent to participate in the clinical trial but are not subsequently assigned to the study intervention. A minimal set of screen failure information is required to ensure transparent reporting of screen failure participants, to meet the Consolidated Standards of Reporting Trials (CONSORT) publishing requirements and to respond to queries from regulatory authorities. Minimal information includes demography, screen failure details, eligibility criteria, and any serious adverse event (SAE).

2.3.2 Treatment Assignment and Randomization/Stratification Procedures

2.3.2.1 Cohorts

Number	Name	Description
1	Mature T-cell malignancies: Dose Escalation	Relapsed/refractory mycosis fungoides/Sézary syndrome, adult T-cell leukemia/lymphoma acute, chronic, and lymphoma subtype (up to 12 evaluable patients)
2	Mature T-cell malignancies: Dose Expansion	Relapsed/refractory mycosis fungoides/Sézary syndrome, adult T-cell leukemia/lymphoma acute, chronic, and lymphoma subtype (up to 9 additional evaluable patients, 12 total evaluable at the MTD)

2.3.2.2 Arms

Number	Name	Description
1	Experimental Treatment: Dose Escalation	IL-15 by CIV infusion at escalating doses of 2 and 4 mcg/kg/day on days 1-5 of each 28-day cycle (max 6 cycles) with mogamulizumab by IV infusion at a dose of 1 mg/kg on days 1, 8, 15, and 22 of cycle 1 and days 1 and 15 of cycles 2-6, to determine MTD

Abbreviated Title: IL-15+Mogamulizumab

Version Date: 11/16/2020

Number	Name	Description
2	Experimental Treatment: Dose Expansion	IL-15 by CIV infusion at the MTD on days 1-5 of cycles 1-6 with mogamulizumab at 1 mg/kg on days 1, 8, 15, and 22 of cycle 1 and days 1 and 15 of cycles 2-6

2.3.2.3 Randomization and Assignment

Treatments assignment is open-label, and non-randomized/non-stratified. Subjects in Cohort 1 are directly assigned to Arm 1; subjects in Cohort 2 are directly assigned to Arm 2.

2.4 BASELINE EVALUATION

The following should be performed within 28 days prior to the first dose of rhIL-15 unless otherwise noted; tests performed as part of screening do not need to be repeated if they were performed within the specified window prior to initiating treatment.

2.4.1 Clinical Evaluations

- Medical history (interim)
- Physical examination including weight, vital signs (i.e., temperature, pulse, respiratory rate, and blood pressure); review of concomitant medications and symptoms/side effects; and assessment of performance status (ECOG performance score, see [APPENDIX A](#))

2.4.2 Laboratory Evaluations

NOTE: Results from outside NIH are accepted

- Required within 7 days:
 - Serum or urine pregnancy test (B-HCG) for women of childbearing potential
- Required within 14 days:
 - CBC with differential and reticulocyte count
 - Chemistry panels including: Acute Care (sodium, potassium, chloride, CO₂, glucose, BUN, creatinine), Mineral Panel (serum calcium, phosphate, magnesium and albumin), Hepatic Panel (alkaline phosphatase, ALT, AST, total and direct bilirubin), and 24-hour urine creatinine clearance (if needed to measure CrCl if serum creatinine >1.5mg/dl)
 - Others: LDH, Uric acid, Total protein
 - Serum Lipase and Amylase
 - Coagulation panel, including: PT/INR and aPTT
 - Iron panel (includes: ferritin, transferrin, iron), folate, vitamin B12
 - C-reactive protein (CRP)
 - Serum Lipase and Amylase
 - TSH, with free thyroxine if TSH is abnormal
 - Urinalysis (with microscopic examination if abnormal)
 - HLA typing (A, B, C, DR, DQ)
 - Soluble IL-2Ra

Abbreviated Title: IL-15+Mogamulizumab

Version Date: 11/16/2020

- Creatinine phosphokinase (CPK), troponin I
- Required within 28 days:
 - Lymphocyte Phenotype: T, B and NK cell subsets
 - Antinuclear antibody (ANA), rheumatoid factor (RF) and anti-thyroid antibody

2.4.3 Imaging Studies

Every participant should have an evaluation of known sites of disease as part of baseline evaluation. **NOTE:** Only results from NIH are accepted

- One or more of the following studies: CT, MRI, FDG-PET and/or clinical photography
- Patients with neurological symptoms or signs should undergo MRI scan* of the brain and lumbar puncture

*NOTE: The MRIs to be done in this study may involve the use of the contrast agent gadolinium, if clinically indicated. The risks associated with MRIs and contrast are discussed in the consent form.

2.4.4 Other Procedures

- Bone marrow biopsy and aspiration to assess lymphoma involvement (within 3 months)
- Selected patients with cutaneous disease (as determined by physician PI or AI) will have clinical photography and dermatology assessment performed to assess their skin disease

2.4.5 Research Correlates

NOTE: See Section 5.1 for additional information. The following sample types will be collected for correlative research studies:

- Required:
 - Blood samples for lymphocyte subset testing and circulating tumor DNA
 - Blood, buccal swab, or saliva for germline DNA
 - Tumor Tissue (archival or fresh)
- Optional:
 - Blood samples for ADCC of mogamulizumab, tissue immune cell subset comparison (as outlined in Section 5.2)
 - Bone marrow biopsy
 - Tumor biopsy is required if archival tissue is not available or adequate; otherwise, this is optional.

3 STUDY IMPLEMENTATION

[figure not shown]
3.1 STUDY DESIGN

In patients with relapsed/refractory MF/SS or ATLL, IL-15 will be administered by continuous intravenous infusion in a dose-escalation 3 + 3 system with a starting dose of 2 mcg/kg/day and a second dose level of 4 mcg/kg/day on days 1-5 of each of six cycles. Mogamulizumab will be

Abbreviated Title: IL-15+Mogamulizumab

Version Date: 11/16/2020

administered IV over at least 1 hour at a dose of 1 mg/kg on days 1, 8, 15 and 22 of cycle 1, and days 1 and 15 of each subsequent cycle. Treatment will continue for a maximum of 6 cycles or until toxicity (i.e., dose limiting toxicity as found in Section 3.1.1 or toxicity requiring hold as defined in Section 3.3) or progressive disease.

3.1.1 Dose Limiting Toxicity

A dose-limiting toxicity (DLT) is defined as: any grade 3, 4, or 5 toxicity if not incontrovertibly due to disease progression or an extraneous cause, and deemed possibly, probably or definitely related to IL-15 or mogamulizumab by the PI or designee during the first 28 days of treatment, with the following exceptions:

3.1.1.1 Hematologic exceptions

- Grade 3 or 4 lymphocytopenia without clinical signs of infection grade 2 or above.
- Grade 3 or 4 neutropenia without clinical signs of infection grade 2 or above.
- Grade 3 or 4 thrombocytopenia lasting fewer than 5 days and not associated with bleeding or purpura.
- Grade 3 leukocytosis (WBC > 100,000/mm³) in the absence of signs of leukostasis or other toxicities possibly related to the expansion of activated cells.

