CTC V4 Grade	1	2	3	4	1	2	3	4	1	2	3	4
Arthritis						1						
Bladder infection		1										
Chills	1	1				2				2		
Constipation	1								1			
Diarrhea	2				1				1	1		
Dizziness					2							
Dry mouth	1				2							
Dry skin						1						
Edema limbs	1	1										
Fatigue	1	1							2	1		
Fever	2	2			1	1			2	2		
Headache	1				1							
Hypotension		1				1			1			
Nausea	2				2				3			
Pulmonary edema		1										
Rash maculo-papular	2								2			
Vomiting	2				1				2			

Abbreviated Title: IL-15+Mogamulizumab

Version Date: 11/16/2020

Table 5: Laboratory abnormalities possibly, probably, or definitely related to research (5-day CIV cohort) excluding single grade 1 events

	3 µg/kg n=4				4 µg/kg n=3				5 µg/kg n=4			
CTC V4 Grade	1	2	3	4	1	2	3	4	1	2	3	4
Anemia			2			2			1	1	1	
ALT increased	1	1			1	1			3			
AST increased		2			2				4			
Alkaline phosphatase		1			1		1		2	1		
Hyperbilirubinemia	1	1				1			1		1	
Hypoalbuminemia		2			1	1			2	2		
Creatinine increased					1				1	2		
Hyperglycemia										1		
Hypernatremia	2										1	
Hyponatremia	1		1		2				3			
Hypocalcemia	1				1				4			
Hypokalemia	2	1							1		2	
Hypomagnesemia					1				3			
Hypophosphatemia		1	2			2				1	2	
Lymphocytosis				2				2			1	2
Lymphopenia		1				1	1			2	1	1
Neutropenia	1				1		1			1		
Thrombocytopenia		2			2				1	1		
Leucopenia		2				1	1		1	1	1	

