3.1.1.2 Non-hematologic exceptions

- Transient (< 24 hours) grade 3 hypoalbuminemia, hypokalemia, hypomagnesemia, hyponatremia or hypophosphatemia which responds to medical intervention.
- Non-sustained (< 7 days) grade 3 liver function test (ATL, AST, alkaline phosphatase, total or direct bilirubin) abnormalities in the absence of clinical signs of hepatic dysfunction (lethargy, confusion, anorexia, pruritus, tremor); for patients with baseline grade 1 elevations, any increase $\geq 10 \times$ baseline will be considered dose-limiting and these patients will be closely monitored for liver function abnormalities.
- Grade 3 rash (maculo-papular, acneiform, or urticaria); if the rate of grade 3 rashes exceeds the expected rate (10% per mogamulizumab package insert) this will be reported as an unanticipated problem.
- First grade 3 infusion reaction associated with mogamulizumab administration (occurring within 24 hours of the dose).

Management and dose modifications associated with the above adverse events are outlined in Section 3.3. If a DLT is possibly, probably, or definitely related to IL-15 and unrelated or

Abbreviated Title: IL-15+Mogamulizumab

Version Date: 11/16/2020

unlikely to be related to mogamulizumab, patient may continue treatment with mogamulizumab alone if PI or designate deems it to be in the patient's best interest. Any DLT at least possibly related to mogamulizumab will lead to permanent discontinuation of protocol therapy regardless of attribution to IL-15. The same management will apply to an occurrence of any DLT-defining toxicity after the first 28 days of treatment; however, that toxicity will not be deemed a DLT for purposes of dose escalation.

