3.3 DOSE MODIFICATIONS

3.3.1 rhIL-15-specific Adverse Events

Please refer to the Comprehensive Adverse Event and Potential Risk list (CAEPR) for rhIL-15 presented in Section [14.1.2](#).

Dose of rhIL-15 is based on the dose level and patient's weight at the beginning of each cycle, and can only be modified for rounding and/or consistency with prior cycles, and not for adverse events or renal/hepatic dysfunction. Infusion may continue during correction of electrolyte and other laboratory abnormalities listed in Section [3.1.1](#). Infusion may be interrupted for up to two hours each day, but treatment should end 120 (± 1) hours after initiation on Day 1.

Abbreviated Title: IL-15+Mogamulizumab

Version Date: 11/16/2020

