5 CORRELATIVE STUDIES

5.1 SUMMARY

This study will attempt to use rhIL-15 to increase NK cell number and activity, thereby enhancing the ADCC of mogamulizumab in treatment of patients with relapsed and refractory MF/SS and ATLL. ADCC capacity of ex vivo PBMCs will be tested on CCR4-expressing cell lines before, during, and after protocol treatment. CCR4 mutation status will be determined for each patient by batch processing, and correlated with response and survival. Differences in circulating immune cell subsets associated with administration will be followed throughout treatment to both study the effects of combined rhIL-15/mogamulizumab therapy on the immune system, and to identify potential biomarkers that would be predictive of response. With the same goal in mind, immune cell subsets in the tumor microenvironment before and after treatment will be determined using single-cell RNA sequencing.

Sample	Collection Details*	Time Points							Supervising Laboratory/Investigator
		Baseline	C1 D8	C1 D15	C2-6 D1	C2-6 D15	Follow-up [#]		
Blood Samples									
Lymphocyte subset testing	• 2 x 10mL K ₂ EDTA (lavender-top) tubes	X	X	(X)	(X)	(X)	(X) ¹	Immunology section, NIH CC	
ADCC of mogamulizumab	• 3 x 10mL sodium heparin green-top tubes	(X) ²	(X) ²					[name]	
Tissue immune cell subsets (comparison)	• 1 x 5mL sodium heparin green-top tube	(X)		(X)			(X)	[name]	

Abbreviated Title: IL-15+Mogamulizumab**Version Date:** 11/16/2020

Sample	Collection Details*	Time Points						Supervising Laboratory/ Investigator
		Baseline	C1 D8	C1 D15	C2-6 D1	C2-6 D15	Follow-up [#]	
Circulating tumor DNA, plasma banking	• 1 x 10mL K ₂ EDTA tube • 1 x 10mL Streck/BCT tube	X	(X)	X	(X)	(X)	X ³	[name] (Leidos CSL)
PBMC banking	• 2 x 10mL sodium heparin green-top tubes	X	X	X	X	X	X	
Anti-IL-15 antibodies	• 1 x 4mL SST tube	X			X		X ¹	
CCR4 expression	• 2 x 10mL sodium heparin green-top tubes	(X)	(X)		(X)			[name] (Laboratory of Pathology)
CCR4 mutation status	• 2 x 10mL sodium heparin green-top tubes	(X)						
Tissue Samples								
CCR4 expression	• One core biopsy sample in formalin	X**		(X)				[name] (Laboratory of Pathology)
CCR4 mutation status	• One core biopsy sample in formalin	X**		(X)				[name] (Laboratory of Pathology)

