14.1.8 Toxicity

The Comprehensive Adverse Event and Potential Risks List (CAEPRs) for Recombinant Human IL-15 provides a single list of reported and/or potential adverse events (AE) associated with the agent using a uniform presentation of events by body system. In addition to the comprehensive list, a subset, the Specific Protocol Exceptions to Expedited Reporting (SPEER), appears in a separate column and is identified with bold and italicized text. This subset of AEs (SPEER) is a list of events that are protocol specific exceptions to expedited reporting to NCI (except as noted below). Refer to the 'CTEP, NCI Guidelines: Adverse Event Reporting Requirements' http://ctep.cancer.gov/protocolDevelopment/electronic_applications/docs/aeguidelines.pdf for further clarification. The CAEPR does not provide frequency data; refer to the Investigator's

Abbreviated Title: IL-15+Mogamulizumab

Version Date: 11/16/2020

Brochure for this information. Below is the CAEPR for Recombinant Human IL-15.

Version 1.3, January 2, 2019*

Adverse Events with Possible Relationship to Recombinant Human IL-15 (CTCAE 5.0 Term)	Specific Protocol Exceptions to Expedited Reporting (SPEER)
BLOOD AND LYMPHATIC SYSTEM DISORDERS	
Anemia	Anemia (Gr 2)
Bone marrow hypocellular	
CARDIAC DISORDERS	
Sinus tachycardia	Sinus tachycardia (Gr 2)
GASTROINTESTINAL DISORDERS	
Abdominal pain	
Diarrhea	
Nausea	Nausea (Gr 2)
Vomiting	Vomiting (Gr 2)
GENERAL DISORDERS AND ADMINISTRATION SITE CONDITIONS	
Chills	Chills (Gr 2)
Edema limbs	
Fatigue	Fatigue (Gr 2)
Fever	Fever (Gr 2)
Injection site reaction	
INFECTIONS AND INFESTATIONS	
Sepsis	
INVESTIGATIONS	
Alanine aminotransferase increased	
Aspartate aminotransferase increased	
Blood bilirubin increased	
Creatinine increased	
Lymphocyte count decreased	Lymphocyte count decreased (Gr 2)
Lymphocyte count increased	
Neutrophil count decreased	
Platelet count decreased	
White blood cell decreased	
METABOLISM AND NUTRITION DISORDERS	
Hypoalbuminemia	
Hypophosphatemia	Hypophosphatemia (Gr 2)
MUSCULOSKELETAL AND CONNECTIVE TISSUE DISORDERS	
Generalized muscle weakness	
NERVOUS SYSTEM DISORDERS	
Dizziness	
Headache	
RESPIRATORY, THORACIC AND MEDIASTINAL DISORDERS	
Dyspnea	
SKIN AND SUBCUTANEOUS TISSUE DISORDERS	
Dry skin	
Erythema multiforme	Erythema multiforme (Gr 2)
Skin and subcutaneous tissue disorders - Other (rash)	
VASCULAR DISORDERS	
Capillary leak syndrome	

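### The DLT exceptions in Section 3.1.1.1 omit lymphocyte count increased, an expected rhIL-15 effect, so related grade 3-4 lymphocytosis is dose-limiting as written

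*Combined protocol and SAP*

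**What the plan says.** Section 3.1.1 defines a DLT as "any grade 3, 4, or 5 toxicity if not incontrovertibly due to disease progression or an extraneous cause", at least possibly related to IL-15 or mogamulizumab, in the first 28 days. Only listed exceptions escape.

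The hematologic exceptions in Section 3.1.1.1 are:
- "Grade 3 or 4 lymphocytopenia without clinical signs of infection grade 2 or above";
- grade 3-4 neutropenia under the same infection condition;
- grade 3-4 thrombocytopenia lasting under 5 days without bleeding or purpura;
- grade 3 leukocytosis, defined by WBC above 100,000/mm3, "in the absence of signs of leukostasis or other toxicities possibly related to the expansion of activated cells".

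The non-hematologic list in Section 3.1.1.2 says nothing about lymphocytes. It closes by extending the consequences beyond cycle 1: "The same management will apply to an occurrence of any DLT-defining toxicity after the first 28 days of treatment". Such a later event does not count for escalation. Section 3.3.1 leaves no room to reduce the rhIL-15 dose, which "can only be modified for rounding and/or consistency with prior cycles, and not for adverse events or renal/hepatic dysfunction".

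Three places mark lymphocyte expansion as expected. Section 5.1 gives the aim: "This study will attempt to use rhIL-15 to increase NK cell number and activity". The rhIL-15 risk list in Section 14.1.8 includes "Lymphocyte count increased". Table 5 in Section 1.2.5.1, titled "Laboratory abnormalities possibly, probably, or definitely related to research (5-day CIV cohort) excluding single grade 1 events", has a lymphocytosis row with grade 3-4 entries at 3, 4 and 5 mcg/kg.

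**The concern.** The exceptions cover a fall in lymphocytes and a very high total white count, but not a rise in lymphocytes, which is what rhIL-15 is given to produce. The MTD is a primary endpoint and rests on counting DLTs in three to six patients per level, so one unlisted but expected laboratory event can decide it.

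There are two ways to go wrong. If the rule is followed literally, two patients with grade 3-4 lymphocytosis at level 2 make 4 mcg/kg the maximally administered dose and send the expansion cohort to 2 mcg/kg. Two at level 1 leave no lower level in Table 6. In later cycles the same event could end rhIL-15, or all protocol therapy if mogamulizumab is thought possibly responsible. If instead the investigator decides that lymphocyte expansion is not a toxicity, a level is cleared by an exception that the protocol does not contain, and a reader of the results cannot tell which rule was applied.

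**Working it through.** **Setting the lists side by side.** Table 5 is read by printed column.

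| Laboratory change | In rhIL-15 risk list (14.1.8) | Grade 3-4 in Table 5 | Exempt in 3.1.1.1 |
|---|---|---|---|
| Lymphocytes down | yes | yes | grade 3-4, conditional |
| Neutrophils down | yes | yes | grade 3-4, conditional |
| Platelets down | yes | none | grade 3-4, conditional |
| Leukocytosis | no | no row | grade 3, conditional |
| Lymphocytes up | yes | yes, 7 entries | no |

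The protocol exempts the expansion term that its own data do not show, and omits the one that they do.

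**Reproducing the plan's figure.** A level is cleared with 0 of 3 DLTs, or with 1 of 3 followed by 0 of 3. For a true DLT rate p:

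f(p) = (1-p)^3 + 3p(1-p)^2 x (1-p)^3 = (1-p)^3 + 3p(1-p)^5

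At 10% to 60% this gives 0.906, 0.709, 0.494, 0.309, 0.172 and 0.082, matching the Section 10.2 table (0.91, 0.71, 0.49, 0.31, 0.17, 0.08).

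**Rates from Table 5**, assuming each count is one patient: at 3 mcg/kg, 2 of 4 (both grade 4); at 4 mcg/kg, 2 of 3 (both grade 4); at 5 mcg/kg, 3 of 4 (one grade 3, two grade 4). The total is 7 of 11, six of them grade 4. No 5-day rate is given for 2 mcg/kg.

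**Illustration: every such event is a DLT and nothing else is.**
- At 2/3: f = 1/27 + 2/243 = 11/243 = 0.045. The exact (Clopper-Pearson) 95% interval for the rate is 0.094 to 0.992, so f runs from 0.915 to below 0.001.
- At 7/11: f = 0.048 + 0.012 = 0.060. The interval is 0.308 to 0.891, so f runs from 0.478 to 0.001.
- Level 2 is the top level, and Table 7 asks for at most 1 DLT in 6 at a recommended dose: g(p) = (1-p)^6 + 6p(1-p)^5. At 2/3, g = 1/729 + 12/729 = 13/729 = 0.018, with a range of 0.897 to below 0.001.

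**Sensitivity to the table's columns.** The table was machine-read. If the row sits one column too far right, the entries become two grade 3 at 3 mcg/kg, two grade 3 at 4 mcg/kg, and one grade 2 and two grade 3 at 5 mcg/kg. The rate at 4 mcg/kg stays 2/3. The pooled rate becomes 6/11, with f = 0.094 + 0.032 = 0.126. The grades change completely: an exception limited to grade 3 covers 1 of 7 events as printed, but 6 of 6 under the shift.

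**The case against.** The best reply is about intent. The leukocytosis exception speaks of expansion of activated cells. If lymphocytosis were separately dose-limiting, a white count above 100,000/mm3 made up mainly of lymphocytes would be exempt under one term and a DLT under the other. On this reading the authors meant to tolerate expansion, and only the wording needs clarifying. The earlier 5-day cohorts went up to 5 mcg/kg despite grade 3-4 lymphocytosis in 2 of 4 patients at 3 mcg/kg, which suggests that lymphocytosis was not treated as dose-limiting there, although that trial's DLT rules are not shown. This stands as evidence of intent. It does not alter the text, and the clash it describes is itself the inconsistency.

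A second reply is that an asymptomatic count is not a toxicity. The exception lists answer this: they name laboratory changes that need not cause symptoms, so the plan treats them as in scope.

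A third is that the list may be deliberately narrow for a new combination. Table 5 also prints grade 3 anemia (two at 3 mcg/kg, one at 5) and grade 3 leucopenia (one at 4, one at 5), and neither is exempt. That is possible, but neither is the effect the drug is given to produce, and the sponsor has already exempted expansion under another term.

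A fourth is that the probabilities carry little weight. That is accepted. They rest on 2 of 3 patients treated without mogamulizumab and graded by CTC v4, with timing against the 28-day window not shown.

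**Conclusion.** The point holds on the wording. As written, related grade 3-4 lymphocytosis in the first 28 days is a DLT, and later it could end rhIL-15. The defect bears on a primary endpoint and is cheap to correct, so it should be fixed before level 2 is judged.

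A reader might infer that escalation is likely to fail. The documents do not support that. The clearing probability at 4 mcg/kg ranges from about 0.92 to nearly 0, it assumes that counts are patients and that the rule is applied literally, and an investigator may well not apply it so.

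A reader might also infer that grade 4 must be exempted because most printed entries are grade 4. That rests on column positions in a machine-read table, and the documents give no grade cut-offs for this term.

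Nor does it follow from Section 6.1.2.1, which does not list DLT status among the conditions that make a laboratory value an adverse event, that such a DLT would be lost. Investigator judgement is one of those conditions, Sections 10.4.2 and 10.4.4 report laboratory shifts and toxicities, and the MTD is unaffected.

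**What to change.** Before level 2 is judged, add one line to Section 3.1.1.1: Grade 3 lymphocyte count increased "in the absence of signs of leukostasis or other toxicities possibly related to the expansion of activated cells". This matches the grade limit and the proviso of the leukocytosis exception.

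The sponsor should also check the Table 5 lymphocytosis grades against their source and then state whether grade 4 is exempt. This second step is needed: if the printed grades are right, the grade 3 line alone would leave both events at 4 mcg/kg dose-limiting. Keeping grade 4 dose-limiting is a legitimate choice, provided that it is stated.

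The cost is that asymptomatic grade 3 lymphocyte expansion alone would no longer stop escalation in a new combination. Expansion with leukostasis or other related toxicity still would. The Section 10.2 table and the sample size do not change.
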